This will be a double-blinded, randomized, controlled intervention with three arms preceded by an open-label 1-week run-in period. This is a multi-center trial with the Cleveland Clinic being the leading site. After screening and consent, all eligible patients will have their first visit at the Clinical Research Unit to start the open-label challenge of carvedilol at a dose of 3.125 mg twice daily. The patient will be monitored for at least 3 hours and if a patient tolerates this dose (assessed by symptoms and vital signs including blood pressure and pulse), a patient will then be discharged home to continue on the drug at 3.125 mg twice daily for the remainder of the week. Patients will receive a follow up phone call the day after their first randomization visit. Patients will be provided with a blood pressure monitor for home and will measure their blood pressure and pulse as directed, and will be contacted daily during the first week to check on vital signs and symptoms. Patients who are able to complete the 1-week run-in phase without adverse effects will return to clinic for assessment by history and physical exam. Stable patients will be randomized to one of three arms for 24 weeks of treatment with placebo, fixed low-dose Carvedilol, or dose-escalating carvedilol to maximum tolerated dose. The first group will receive a placebo drug for the remainder of the study. The second group will continue with carvedilol at a dose of 3.125 mg twice daily. The third group of patients will receive carvedilol 3.125 mg twice daily one week, then 6.25 mg twice daily for second week, 12.5 mg twice daily for third week with the option to increase to the maximal dose of 25 mg bid for the remainder of the study period. If a dose is not tolerated, the dose will be decreased to the prior week's tolerated dose for the remainder of the study. Subjects will receive weekly phone calls after starting the study and a study visit at weeks 1, and months 1, 3 and 6 to evaluate for side effects, to monitor clinical status, and to collect outcome data. Patients will be provided a home blood pressure monitoring device and asked to record pulse and blood pressure in the morning and evening with instructions to call at any time if systolic BP<85 mm Hg or pulse<55, or if there is any adverse event such as hospitalization or unscheduled doctor visits.

B. Population

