Final eligibility will be determined by the investigator after review of the medical record and data gathered during the screening visit. Eligible, enrolled subjects will undergo additional baseline procedures:

- Quality of life questionnaires
- Fasting Gated FDG-PET scan
- Echocardiography
- Blood draw for flow cytometry, plasma nitrite and nitrate, global arginine bioavailability ratio (GABR), Erythropoietin, & NT-proBNP
- Urine for nitrate
- Exhaled NO

E. Intervention

Open-label Run-in Phase

All enrolled, eligible subjects will receive an open-label carvedilol therapy at starting dose of 3.125 mg twice daily for one week and be monitored at the Clinical Research Unit for the first-dose challenge of Carvedilol. Upon discharge, enough carvedilol to complete the 1-week run-in period will be dispensed by a licensed provider. Subjects will be instructed to return in 1 week with any

unused medication. Those individuals who are eligible for randomization to the trial will undergo the procedures summarized in Table A1 “Run-in Week”.

Double-blinded Randomized Phase

At the end of the 1-week run-in phase, subjects who have tolerated the low-dose carvedilol without severe or limiting side effects, still meet the inclusion and exclusion criteria, and who wish to continue in the study will be randomized to one of three arms: placebo, low-dose carvedilol, or escalating dose carvedilol for 6 months. Subjects and the investigators will be blinded to their group assignment for the duration of the study.

- Group 1 will receive a placebo drug to take twice daily for 6 months.
- Group 2 will receive carvedilol at a dose of 3.125 mg twice a day for 6 months.
- Group 3 will receive carvedilol in a dose escalation scheme. They will be given 3.125 mg tablets to take bid for 1 week, followed by 6.25 mg bid for 1 week, followed by 12.5 mg bid for 1 week with the option to increase to the max dose of 25 mg bid for the remainder of the study. During up titration, if a dose is not tolerated, the dose will be decreased to the previous tolerated dose for the remainder of the study.

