Subjects will be scheduled for follow-up visits at week 1, and months 1, 3, and 6. There is no scheduled follow-up of subjects after completion of the exit visit; subjects will then resume their standard of care clinical course. If patients were on carvedilol, the option to remain on therapy will be allowed based on patient and physician preference. If removal from therapy is requested by patient or physicians caring for the patient, carvedilol dose will be reduced by half every week until the patient is on 3.125 mg twice daily, at which time drug will be stopped.

At follow-up visits, subjects will bring their medications to check for compliance and correct dosage. At each visit, the subjects will undergo a physical exam including BP and pulse, pregnancy test, EKG, breathing tests, 6-minute walk, and echocardiogram, fill out questionnaires, and give a blood and urine sample. Please see Table A1 below for details.

At the study teams discretion and for patient's convenience study visits Screening Baseline and Run in may be combined.

G. Data Collection

Outcome data will be collected at the baseline visit and at follow-up visits at week 1, and months 1, 3 and 6. Safety monitoring parameters will be collected at all visits and via weekly phone calls throughout the study period.

Table 1. Procedures Performed at Each Visit

Procedure	Screening	Baseline	Run-in Week	Month 1	Months 3 & 6 (or upon study exit)
Chest X-ray	X*				
Blood draw for CBC, Complete metabolic panel, HIV, Hepatitis	X				
Blood draw for Erythropoietin		X			X
Cardiac-gated fasting FDG-PET		X			X (6 month only)
Blood draw for flow cytometry, plasma nitrite & nitrate, and GABR		X	X	X	X
Urinary nitrate		X	X	X	X
Exhaled NO		X	X	X	X
Saliva Collection		X			X (6 month only)
Quality of Life Questionnaires	X	X			X
Blood draw for NT-proBNP		X	X		X
Six Minute Walk Test	X		X		X
Echocardiogram		X	X		X
Electrocardiogram	X		X	X	X
Urine pregnancy test**	X	X	X	X	X

Spirometry & Diffusion capacity	X		X		X
Anticipated length of visit:	1 hour	5 hours	2 hours	2 hours	5 hours

*if not done in past year

**only women of child-bearing age

*** screening, baseline, run-in may be combined

Blood draws

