Baseline characteristics will be reported, including age range and the proportions that are female, postmenopausal, and Caucasian. Means and standard deviations or medians and interquartile range will be reported for all continuous data, and non-continuous data will be reported as percentages. A log transformation may be utilized for any data that is not normally distributed. The three randomized study groups will be compared, based on the intent-to-treat principle, with respect to changes from baseline. Repeated measures analysis of variance will be used to compare groups using data from all time points together, though T-tests will also be used to compare pairs of groups with respect to differences between pairs of time points. Using actual administered doses, relationships between dose and changes over time will also be explored using appropriate linear or non-linear models to estimate dose-response relationships. Reports of blinded group summaries of adverse events will be regularly produced for safety monitoring.

b. Confidentiality

To maintain patient confidentiality, all study data will be de-identified. Each subject, upon enrolling in the study, will be assigned a three-digit subject number. Case report forms and the study database will identify each subject only by subject number and will contain no patient identifiers. De-identified case report forms will be kept within study binders, kept in a locked filing cabinet in a locked room. Completely de-identified study data will be stored in a data table maintained on a password-protected computer and stored on the Cleveland Clinic network, which is regularly backed up. The code identifying which patient belongs to each subject number will be kept in a separate locked filing cabinet in a locked room. Only the study coordinator and investigators will have access to this code.

REFERENCES

1. ATS statement: guidelines for the six-minute walk test. Am J Respir Crit Care Med 2002;166:111-7.

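### The repeated measures ANOVA names neither its visits nor the effect tested; if the run-in week counts as follow-up, a time-averaged arm comparison of the NO, β-AR and several secondary measures is diluted

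*Combined protocol and SAP*

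**What the plan says.** Data Analysis/Reporting, a. Analysis Plan, compares the randomized groups by intention to treat on changes from baseline: "Repeated measures analysis of variance will be used to compare groups using data from all time points together". It adds pairwise t-tests between pairs of time points. It gives no list of visits and does not say whether the group effect or the group-by-time effect is the test.

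Data Collection states: "Outcome data will be collected at the baseline visit and at follow-up visits at week 1, and months 1, 3 and 6". Table 1 has columns for Screening, Baseline, Run-in Week, Month 1, and Months 3 and 6. Only Run-in Week can be week 1.

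Intervention, Open-label Run-in Phase, places that column before randomization: "Those individuals who are eligible for randomization to the trial will undergo the procedures summarized in Table A1". The next subsection begins the randomized phase: "At the end of the 1-week run-in phase, subjects who have tolerated the low-dose carvedilol without severe or limiting side effects" go on to be randomized.

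Table 1 marks Run-in Week for flow cytometry, plasma nitrite and nitrate, GABR, urinary nitrate, exhaled NO, NT-proBNP, walk test and echocardiogram. It does not mark it for erythropoietin, FDG-PET or quality of life.

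Study Design, after describing the randomized dosing, mentions "a study visit at weeks 1, and months 1, 3 and 6 to evaluate for side effects". This could mean a week-1 visit after randomization, but Table 1 has no such column.

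**The concern.** At the run-in visit all patients are on the same drug and dose and have no assigned arm, so the expected difference between arms is zero. Averaging that zero with the post-randomization visits pulls the arm difference towards zero. The NO and β-AR markers belong to the Primary Aim of a mechanistic trial, where the size of the marker effect is itself a result. With the effect unnamed, one analyst could report a diluted average and another an undiluted comparison, both citing the same sentence.

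**Working it through.** **The plan's own figure.** The Sample Size section gives 14 per group for 90% power at α = 0.025 (taken as two-sided), a 50% lower median and a CV of at most 50%. The difference is ln 2 = 0.693. With log SD = √ln(1 + 0.5²) = 0.472, the noncentral t gives 92.6% power; with SD = 0.5 it gives 89.4%. The figure is reproduced. It rests on the FDG-PET t-test and not on the ANOVA.

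**Share of the effect kept.** With k post-randomization visits and one run-in visit of zero expected difference, the time-averaged difference is k/(k+1) of the mean post-randomization difference, whatever the correlation.
- NO and β-AR markers (run-in, months 1, 3, 6): 3/4.
- NT-proBNP, echocardiogram, walk distance (run-in, months 3, 6 by Table 1): 2/3. If echocardiogram and walk are also done at month 1, as the Follow-up Schedule says ("At each visit, the subjects will undergo a physical exam including BP and pulse, pregnancy test, EKG, breathing tests, 6-minute walk, and echocardiogram"), they too keep 3/4.

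**Power.** The documents give no effect size or correlation for these measures, so these inputs are assumptions: 14 per arm, a constant effect of 1 SD in both active arms after randomization, α = 0.05, and a 2-df test on the mean change from baseline.

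λ = n·Σ(eᵢ − ē)²/SD². For effects (0, f, f), λ = 14 × (2/3) × f²/SD² = 9.33·f²/SD², where f is the share kept (1 without run-in). Under compound symmetry with m visits averaged, SD² = (1 + (m−1)r)/m + 1 − 2r.

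At r = 0.5:
- 3/4 schedule. With run-in, SD² = 0.625 and λ = 9.33 × 0.5625/0.625 = 8.4. Without, SD² = 0.667 and λ = 14.0.
- 2/3 schedule. With run-in, SD² = 0.667 and λ = 9.33 × 0.444/0.667 = 6.2. Without, SD² = 0.75 and λ = 12.4.

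For AR(1), visits are placed at 0, 0.25, 1.25, 3.25 and 6.25 months (the 2/3 schedule omits 1.25). Power with vs without run-in, with the loss taken before rounding:

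| Correlation | 3/4 kept | Loss | 2/3 kept | Loss |
|---|---|---|---|---|
| Compound symmetry 0.3 | 55% vs 78% | 23 | 43% vs 73% | 30 |
| Compound symmetry 0.5 | 70% vs 91% | 20 | 57% vs 87% | 30 |
| Compound symmetry 0.7 | 91% vs 99% | 8 | 80% vs 98% | 18 |
| AR(1), monthly 0.5 | 66% vs 72% | 7 | 51% vs 58% | 7 |
| AR(1), monthly 0.7 | 78% vs 82% | 5 | 60% vs 65% | 5 |
| AR(1), monthly 0.95 | ~100% vs ~100% | 0 | 99% vs ~100% | 0 |

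The two structures differ because under AR(1) a value taken one week after baseline is highly correlated with baseline. Including it reduces the variance of the mean change almost as much as it reduces the effect.

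**Group-by-time with baseline as a level.** For two arms and a constant effect, the interaction sum of squares is 3 − 9/4 = 0.75 without run-in and 3 − 9/5 = 1.2 with it. The run-in visit helps this test.

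**Month-6 pairwise contrast, 1 SD effect.** The unadjusted change has SD √(2 − 2ρ); the baseline-adjusted value has SD √(1 − ρ²), where ρ is the baseline-to-month-6 correlation.
- Compound symmetry, ρ = 0.5: SD 1.00 vs 0.866; power 72% vs about 83%.
- AR(1), monthly 0.7, ρ = 0.7^6.25 = 0.108: SD 1.336 vs 0.994; power 48% vs 73%.

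**The case against.** The strongest reply is that the harm is conditional at each step. The plan never names the run-in visit for this ANOVA, and Study Design can be read as meaning a post-randomization week 1. A group-by-time test with baseline as a level, a natural reading of repeated measures ANOVA, gains from the run-in visit. Under AR(1) little power is lost. The plan also has an unaffected month-6 contrast, through the Sample Size section and the pairwise t-tests. All of this stands and limits the point. It does not settle which visits and effect the ANOVA uses, and it does not remove the 25% or 33% shrinkage of a time-averaged estimate.

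A post-randomization week 1 would not make the visit fully informative either. In that week the low-dose and escalating arms are on the same dose ("The third group of patients will receive carvedilol 3.125 mg twice daily one week"), so it cannot separate those two.

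A reader might infer three stronger things that the documents do not support:
- That the trial needs 23 or 27 per arm instead of 14 to recover the lost power. Those figures hold only under compound symmetry at r = 0.5.
- That the plan could lead to a test with about 5% power. That requires a group-by-time test on post-randomization change scores with the run-in dropped, whereas the text keeps all time points. With the run-in kept, the same test has 79% power at r = 0.5 in simulation.
- That the primary comparison is compromised. Neither co-primary is measured at run-in.

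**Conclusion.** The point holds in conditional form. The ANOVA sentence leaves visits and tested effect open, and the most direct reading of Data Collection with Table 1 brings in a pre-randomization visit. If that visit counts as follow-up in a time-averaged group test, the estimate is 3/4 of the mean post-randomization effect for the NO and β-AR markers and, by Table 1, 2/3 for NT-proBNP, echocardiography and walk distance. This shrinkage needs no correlation assumption.

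The power loss does need one. With 14 per arm, a 1 SD effect in both active arms and α = 0.05, it is about 8 to 23 points (3/4 kept) or 18 to 30 points (2/3 kept) under compound symmetry with r = 0.3 to 0.7, and about 0 to 7 points under AR(1) with monthly r = 0.5 to 0.95. The run-in visit does not affect the co-primaries, the baseline-to-month-6 contrasts or type I error. The change should be made because a better analysis costs almost nothing, not because the main conclusion is at risk.

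**What to change.** In the Analysis Plan:
1. State that the run-in value is a pre-randomization measurement. Report it descriptively or use it as an optional covariate, where the gain is small (month-6 pairwise power 83% to 85% in simulation at compound symmetry r = 0.5). Do not count it as a follow-up outcome.
2. Compare arms over post-randomization visits with a mixed model with arm, visit and arm-by-visit terms, adjusted for the pre-drug baseline in place of unadjusted change scores.
3. Name the month-6 contrast as the effect reported. The Sample Size section already measures change to month 6.

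Reconcile week 1 across Study Design, Follow-up Schedule, Data Collection and Table 1. Two wording matters can be settled in the same edit but add no weight to the point. First, whether echocardiogram and walk are done at month 1. Second, since "study visits Screening Baseline and Run in may be combined", say that the baseline value is the pre-drug one, and that there is no separate run-in covariate when those visits are merged.

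The cost is wording and slightly more analysis work, with no added visits, samples or patients.

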indicates no significant adverse effect on clinical functional status (NYHA class, walk distance, cardiac output, pulmonary artery pressure, pulse, blood pressure). Thus, we propose to determine whether treatment with a β -blocker reverses biochemical abnormalities in PAH that lead to maladaptive right ventricular remodeling and failure, utilizing a blinded, placebo-controlled, randomized trial of carvedilol in PAH patients for six months. We will also evaluate clinical parameters of cardiovascular function in relation to changes in the biochemical effects of treatment. Because PAH patients ultimately die of heart failure, carvedilol was chosen as the β -blocker in this study, as it is one of the two β blockers currently FDA-indicated for the treatment of heart failure, and has been extensively well-studied for use in very severe heart failure. Carvedilol blocks $\beta 1AR$ and $\beta 2AR$, as well as $\alpha 1AR$, the latter blocks vasoconstriction and may benefit for PAH patients by decreasing afterload. Additionally, carvedilol is inexpensive and generally well-tolerated; specifically, during long term treatment, intolerance to drug in patients with severe heart failure (class III-IV) did not differ from patients with mild-to-moderate heart failure (class II).

Specific Aims and Hypothesis

We hypothesize that use of carvedilol in patients with PAH will reverse loss of, and resensitize β -adrenoreceptors, increase production of NO, and reduce activation of HIF-1 α , which altogether will improve right and left ventricular function, decrease right and left ventricular size, and improve exercise and functional capacity. To test this, we propose a blinded, placebo-controlled, randomized trial of carvedilol at a fixed low-dose or dose-escalating pattern of therapy in PAH patients for six months with a one-week open-label run-in phase.

A. Primary Aim

To determine whether treatment with carvedilol reverses biochemical abnormalities associated with PAH, we will assess the following:

- Activation of HIF-1 α (co-primary end points):** We will assess activation of HIF-1 α via measurement of plasma erythropoietin and myocardial glucose uptake during fasting gated FDG-PET. We already know that erythropoietin is elevated in PAH and that FDG-uptake is high. We expect both to decrease on drug.

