Target enrollment for this study will be 68 patients. The primary outcomes FDG-PET uptake and erythropoietin, are anticipated to have positively skewed distributions, amenable to the use of ratios of 6-month measures relative to baseline to measure changes over time. Log transformed ratios are then anticipated to have approximately normal distributions. For secondary measures demonstrating less skewness or even approximate normality without the log transformation, absolute changes from baseline to 6 months will be used to measure change over time. Sample size is determined taking into account the power of the T-test for comparing the placebo and low dose carvedilol groups with respect to the reduction in FDG-PET uptake, as measured by the ratio of 6-month uptake to baseline uptake. Variability in FDG-uptake measures over 6 months suggests an expectation that the coefficient of variation in uptake ratios will not exceed 50%. Using a Bonferroni correction to adjust for multiple time points with $\alpha=0.025$, the T-test comparing log-ratios has 90% power to detect a difference in groups such that ratios have a 50% lower median for the low dose carvedilol group relative to the placebo group, if the groups contain $n=14$ subjects each. This effect size was selected based on previously observed reductions in FDG-PET uptake of roughly 50% among patients on β -blocker. Considering 10% potential dropout after randomization and a 30% potential dropout during the run-in phase, we intend to enroll 68 patients into the run-in phases, to achieve at least 48 patients eligible for randomization into the placebo, low dose Carvedilol, or dose escalation groups.

D. Enrollment

Recruitment Strategy

Patients who are diagnosed with PAH will be identified as potential subjects by either a nurse or doctor involved in the patient's disease management. These patients will be referred to the study investigators for screening and to obtain informed consent. Subjects will be recruited as they become available and without regard to gender, race, or ethnicity.

Informed Consent

All volunteers will be approached by the study investigators or their designee. The consent interview will take place the day of a patient visit to the Pulmonary Department. In a private examination room, one of the research investigators will explain the details of the study, to the

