Because study physicians are blinded to groups, if patients are determined to be intolerant of drug (based on symptoms, signs such as sitting systolic BP<85 mm Hg or resting pulse<50, or severe adverse event such as hospitalization for heart failure), a request for dose reduction to the prior week will be requested from the research pharmacist ([name]), who is aware of treatment assignment. He will provide a new week's worth of medications at the “lower” dose. In the case of placebo, placebo will again be provided. In the case of fixed low-dose of carvedilol, placebo will be provided. In the case of dose-escalating carvedilol, the prior week's dose will be provided. Regardless of changes in dose, all three randomized study groups will be compared, based on the intent-to-treat principle, and thus subjects will be maintained in their original assigned study group for analyses.

Randomization scheme

Blocked randomization will be used. The block sizes will also be random and known only to the research pharmacist ([name], Cleveland Clinic Research Pharmacy), who will perform the randomization and know treatment assignment at time of enrollment. The research pharmacist will ensure that a disproportionate subclass (idiopathic, familial or associated PAH) and/or severity of PAH are not entered into any single arm of the study.

Blinded Medication Dispensing

After randomization, all subjects will receive the study medication/placebo for the first 4 weeks in 4 separate bottles labeled “week 1,” “week 2,” “week 3” and “week 4” to blind subjects to whether they are assigned to the dose escalation group. All pills will be encapsulated so that dosing or medication cannot be discerned by patients or study investigators. Enough medication/placebo will be dispensed to last until the next scheduled follow-up visit. Subjects will be instructed to bring all unused medication and the medication bottles (even if empty) to each follow-up visit.

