Doppler echocardiography will be performed by a single well-experienced echo technologist ([name]) for all studies to estimate PAP, RV and LV function using previously validated methods. Right ventricular function will be assessed via measurement of RV fractional area change (RVFAC), RV ejection fraction, myocardial performance index (MPI) of the RV, tricuspid annular plane systolic excursion (TAPSE), tissue Doppler-derived systolic velocity of the lateral tricuspid annulus (S' velocity), three-dimensional RV ejection fraction, and longitudinal strain and strain rate with tissue Doppler techniques (conventional technique, 2-dimensional speckle tracking and velocity vector imaging). Among these methods, the most used parameters are RVFAC, TAPSE, S' velocity of the lateral tricuspid annulus, and RV MPI.

Exhaled NO measurement

The participant will take in a deep breath and exhale through a mouthpiece attached to the nitric oxide analyzer (Aerocrine). This will be repeated for a total of three exhaled NO readings. NO is measured using the American Thoracic Society recommended guidelines.

FDG-PET scan

Cardiac-gated fasting FDG-PET scans will be conducted on fasting patients at baseline and 6 months. Finger stick blood sugar will be measured to assure fasting state (blood sugar < 120 mg/dl). Patient data will be acquired using a clinical PET/CT scanner (Biograph mCT 128) having time-of-flight capable PET detectors. First, a low-dose CT scan will be acquired to provide an attenuation map for PET data corrections. Then, a PET scan will be acquired in list mode for fifteen minutes with ECG signals obtained during the scan. Both static and gated images will be reconstructed using advanced iterative algorithms available on the scanner. All subjects will be fasting 8 h prior to and during the study, then injected with 370 MBq (10 mCi) FDG and scan performed at 1.5 h post-injection. Images will be analyzed in a blinded fashion by [name] using an image fusion workstation (MSViewer, CPS Innovations, Knoxville, TN) with region-of-interest (ROI) measuring tools. A total of five ROI will be measured in heart (left & right atria, RV, LV and IVS). In addition, ROI will be measured for the blood pool of the thoracic aorta. FDG uptake depends on factors including time between injection and scan, blood glucose, and body mass. For consistency, relative uptake will be normalized to blood pool FDG in thoracic aorta.

Safety and tolerability outcomes

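### The plan names repeated measures ANOVA but does not say how patients with missing visits or early-exit samples enter it; a likelihood-based mixed model on all observed values should be specified

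*Combined protocol and SAP*

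**What the plan says.** The Combined protocol and SAP, section G. Data Analysis/Reporting, a. Analysis Plan, sets the principle: "The three randomized study groups will be compared, based on the intent-to-treat principle, with respect to changes from baseline". It then names two methods. The first is longitudinal: "Repeated measures analysis of variance will be used to compare groups using data from all time points together". The second is pairwise: "T-tests will also be used to compare pairs of groups with respect to differences between pairs of time points". It does not say how the repeated measures model is estimated, what covariance it assumes, or what happens to a patient with a missing visit. No other section does either.

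Four other places bear on this:

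- **Section C, Sample Size Rationale and Estimate.** Losses are expected ("Considering 10% potential dropout after randomization"), but they are dealt with only by enlarging the sample.
- **Section E, Double-blinded Randomized Phase.** Intent-to-treat is explained in terms of dose changes: "thus subjects will be maintained in their original assigned study group for analyses". Missing visits are not mentioned.
- **Section H, Early Withdrawal.** Reasons for leaving include unacceptable side effects, non-adherence and needing more than three dose reductions.
- **Table 1.** Erythropoietin, one of the two co-primaries, is taken at baseline and in a last column headed "Months 3 & 6 (or upon study exit". The NO and flow cytometry markers are also taken at the run-in week and month 1. The other co-primary has a single follow-up: "Cardiac-gated fasting FDG-PET scans will be conducted on fasting patients at baseline and 6 months".

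**The concern.** Repeated measures ANOVA in its textbook form needs a value at every visit. A patient with erythropoietin at baseline and month 3 but not month 6 would be left out altogether, month-3 value included, and the comparison would cover completers rather than everyone randomized. A mixed model, which many analysts also call repeated measures analysis, would keep that patient. Two analysts could therefore follow the same sentence, analyse different sets of patients, and both claim to have kept to the plan. Nothing fixes that choice before the data are seen.

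Several of the listed withdrawal reasons concern tolerability, which may well differ between placebo, fixed low dose and escalating dose. If leaving is also related to response, a completer comparison can be biased.

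The exit column adds a gap that does not depend on how ANOVA is read: nothing says whether a sample taken at early exit counts as month 3, month 6 or neither.

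**Working it through.** **1. The plan's own figures.** Inputs from section C: 50% lower median ratio, so a log difference of ln 2 = 0.693; coefficient of variation at most 50%, so log-SD = sqrt(ln(1 + 0.5²)) = 0.472; alpha 0.025 (two-sided assumed); 90% power.

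- The t-test needs 13 per group with SD 0.472 and 15 with SD taken as 0.5. The stated 14 lies between, with power 92.6% and 89.4% respectively.
- Dropout: 14 / 0.9 = 15.6, so 16 per arm, and 3 × 16 = 48 randomized, as stated.

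**2. Power under a complete-case analysis.** 48 × 0.9 = 43.2 patients, or 14.4 per arm. That is the 14 already planned.

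**3. Bias for erythropoietin.** Simulation of 4,000 two-arm trials, 16 per arm. Assumed: log-change SD 0.472 (borrowed from FDG uptake, because none is given for erythropoietin), month-3 to month-6 correlation 0.6, true ratio 0.50. The estimate is the average of months 3 and 6. Patients with the worst month-3 values leave after month 3.

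| Dropout, placebo / active | Complete-case ratio | Log bias, ln(ratio / 0.50) | Likelihood ratio |
|---|---|---|---|
| 10% / 10% | 0.498 | −0.004 | 0.499 |
| 10% / 20% | 0.472 | −0.058 | 0.499 |
| 5% / 15% | 0.471 | −0.060 | 0.499 |
| 20% / 10% | 0.528 | +0.054 | 0.499 |

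A separate run with about 10 to 12% dropout, and response-related selection in the active arm only, gave complete-case bias of −0.023 to −0.049. Likelihood bias was under 0.002, with essentially the same standard error.

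Relative to the planned effect: 0.02 / 0.693 = 3% and 0.06 / 0.693 = 9%. Relative to sampling error: the SD of the two-visit average is 0.472 × sqrt((1 + 0.6) / 2) = 0.422, so with 14 per arm the SE is 0.422 × sqrt(2/14) = 0.160, and 0.06 / 0.160 = 0.38 of one SE.

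**4. A harsher pattern.** Suppose everyone above one fixed month-3 log change leaves, whatever the arm.

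- Cut-off 0.6: placebo loses P(Z > 0.6/0.472) = 10% and active P(Z > 1.293/0.472) = 0.3%. The complete-case ratio is 0.535, a bias of +0.068.
- Cut-off 0.3: placebo loses P(Z > 0.3/0.472) = 26% and active P(Z > 0.993/0.472) = 2%. The ratio is 0.579, a bias of +0.147.

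Both go against carvedilol. The likelihood estimate stays at 0.498 to 0.499.

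**5. Dropout that depends on the unseen month-6 value** (10% / 20%): complete-case 0.471, likelihood 0.485. The mixed model about halves the bias but does not remove it.

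**6. Markers with more visits.** The run-in visit comes before randomization, so Table 1 leaves three post-randomization visits (months 1, 3 and 6). With an assumed 5% missing independently at each, listwise deletion removes 1 − 0.95³ = 14.3% of patients.

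**The case against.** The strongest reply is that the plan never says classical or complete-case. Using data from all time points together describes a mixed model just as well. That stands. A reader might infer that the plan contradicts its own intent-to-treat promise, but the documents do not support this: they use the term to mean analysis by assigned arm after dose changes, and ANOVA does not breach that. What is shown is an unspecified method.

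A reader might also infer that dropout would flatter carvedilol. That is not supported either. Poor responders leaving is not enough, since selection must differ between arms, and the direction depends on the pattern. None of the listed withdrawal reasons refers to erythropoietin, patients and investigators are blinded, and the run-in removes some early intolerance. Dose escalation is concentrated in the first weeks, so some tolerability dropout may come before any post-randomization erythropoietin value exists. A mixed model recovers little for those patients.

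Other points soften the concern. The baseline-to-month-3 t-test keeps later leavers, although the baseline-to-month-6 test does not. Exit samples are collected, and nothing says they would be counted as month 6. Sphericity is not an issue for erythropoietin analysed as two changes from baseline, because it holds automatically with two repeated values.

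None of this supplies the missing rule.

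**Conclusion.** The point holds as a gap in a key analysis, not as a proven contradiction or a proven bias. The plan expects incomplete patients, names a method whose standard form discards them, and gives no rule for them or for exit samples.

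The likely size is modest: about 0.02 to 0.06 on the log scale, in either direction, when dropout proportions or selection differ by arm. It is 0.07 to 0.15 towards no effect under a fixed cut-off, and essentially zero when selection is alike. These figures rest on an SD borrowed from FDG uptake, an assumed correlation (0.6 in the tabulated runs), assumed dropout splits, and dropout placed after month 3 among the worst responders. The planned power is not at risk. The case for acting is that a likelihood-based fit removes nearly all the bias when dropout depends on observed values, at essentially no loss of precision.

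**What to change.** Replace the repeated measures sentence with wording such as:

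> Repeated outcomes are analysed by a likelihood-based linear mixed model for repeated measures, with arm, visit, arm-by-visit and baseline value, unstructured covariance and Kenward-Roger degrees of freedom. All observed post-randomization values from all randomized patients are used, in their assigned arm. The month-6 arm contrast is the estimate. If the model does not converge, compound symmetry is used.

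Then add three rules:

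- **Exit samples.** Assign each to the nearest scheduled visit by pre-set windows based on the actual sampling date, never to month 6 by default. State what happens when two samples fall in one window.
- **FDG-PET.** Keep it as a baseline-to-month-6 comparison. A patient without a follow-up scan has no post-baseline value for a mixed model to use, so report missing scans by arm.
- **Sensitivity analysis.** Add one for dropout that depends on unseen values, for example imputation with a range of shifts by arm, covering both co-primaries.

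The cost is a few sentences, settled before unblinding, and slightly more analysis work in standard software. The one technical risk is non-convergence with about 16 per arm, which the named fallback covers.
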